 WallFlex Pancreatic Pivotal Protocol
 91067616 Rev/Ver AK
 Page 5 of 64

	
deterioration of clinical status and may consist of non-invasive imaging or of a pancreatogram. A pancreatogram will only be performed if an ERCP is necessitated for a reintervention with or without restenting.
 
4. Stent Functionality
 
Stent functionality will be assessed from stent placement until stent removal or observation of complete or partial stent migration.
 
Stent functionality is defined as adequate pancreatic duct drainage reflected by reduction of pain and lack of restenting.
 
5. Izbicki pain scale assessed at each study visit
 
The Izbicki pain scale (see appendix in section 22.1) has four sectors related to severity of pain, frequency of pain, analgesic medication, and disease-related inability to work.
 
6. Average daily narcotic dose for prior month assessed at each study visit
 
7. Maintenance of the VAS Pain Score and Frequency of Pain Score recorded at 6 months post-stent removal compared with that recorded at the time of plastic stent removal, for patients with plastic pancreatic stent indwelling immediately prior to study stent placement
 
Technical Success
 
8. Ability to deploy the stent in satisfactory position (Stent Placement Success). Ease of placement will also be assessed.on a 5 point Likert scale.
 
Satisfactory position is defined as the stent being across the stricture, without visible occluding impaction at the genu of the pancreatic duct and with distal end of the stent visible in the duodenum.
 
9. Successful endoscopic stent removal (Endoscopic Stent Removal Success).
 
Endoscopic stent removal success is defined as ability to remove stent endoscopically (forceps, snare) without serious stent removal-related adverse events. Ease of removal will also be assessed.on a 5 point Likert scale. Use of stent-in-stent removal technique will be considered a removal failure. For patients who experience complete distal migration of the study stent, this endpoint will not be evaluated.
 
Safety and Device Events
 
10. Device Events, including findings not associated with adverse

--	---

August 28, 2017

Boston Scientific
 WallFlex Pancreatic Pivotal Protocol
 91067616 Rev/Ver AK
 Page 6 of 64

	events, such as but not limited to asymptomatic stent migration.

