1.2 Prior Clinical Trials

In addition to the above publications, preliminary data is available from a small 10 patient trial conducted with the Fully Covered WallFlex Pancreatic Stent. Patients with painful chronic pancreatitis of Cremer Type IV were enrolled between June and September 2014. Intended indwell was 3 months in 5 patients and 6 months in 5 patients. In total 14 stents

August 28, 2017

Boston Scientific
WallFlex Pancreatic Pivotal Protocol
91067616 Rev/Ver AK
Page 17 of 64

were placed, with 2 patients having immediate removal and replacement of the initial stent due to deployment in unsatisfactory position and 2 patients needing a second stent placement after premature complete distal migration of the first indwelling stent. Stent migration without symptoms, thought to be a reflection of adequate calibration of the benign stricture, occurred in 6 stent placements, not requiring restenting. Clinically meaningful complete distal migration (CDM) with symptoms occurred in 25% (3/12) of stent placements with intended stent indwell. There were no proximal stent migrations. Endoscopic stent removal was performed per-protocol easily in one patient after a 3 month indwell and in 2 patients after a 6 month indwell without stent removal-related adverse events (AEs). After a median follow-up of 196 days (range 175 - 373) after stent removal or observation of CDM of the stent, 80% (8/10) of patients remained stent-free. Longer term follow-up is ongoing. One patient had premature CDM followed by placement of plastic stents. One patient had no pain relief after SEMS placement and had subsequent pancreatic diversion surgery which did not provide pain relief either. Serious Adverse events (SAEs) occurred in 50% (5/10) of patients, with 7 SAEs (2 pain associated with premature CDM, 2 transient pain related to stent expansion immediately following stent placement, 1 pain unresolved by stenting or subsequent pancreatic diversion surgery, 1 bacterial infection and 1 mild acute pancreatitis). No SEMS needed to be removed due to intolerable pain after SEMS placement. There were no stent-induced ductal changes.

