Recurrence of stricture is defined as need for restenting. Restenting will take place if there is deterioration of clinical status (see definition in secondary endpoint 2 above) and documented recurrent stricture based on imaging. Imaging may be prompted by deterioration of clinical status and may consist of non-invasive imaging or of a pancreatogram. A pancreatogram will only be performed if an ERCP is necessitated for a reintervention with or without restenting.

4. Stent Functionality

Stent functionality will be assessed from stent placement until stent removal or observation of complete or partial stent migration.

Stent functionality is defined as adequate pancreatic duct drainage reflected by reduction of pain and lack of restenting.

5. Izbicki pain scale assesed at each study visit

The Izbicki pain scale (see appendix in section 22.1) has four sectors related to severity of pain, frequency of pain, analgesic medication, and disease-related inability to work.

6. Average daily narcotic dose for prior month assessed at each study visit

7. Maintenance of the VAS Pain Score and Frequency of Pain Score recorded at 6 months post-stent removal compared with that recorded at the time of plastic stent removal, for patients with plastic pancreatic stent indwelling immediately prior to study stent placement

August 28, 2017

Boston Scientific
WallFlex Pancreatic Pivotal Protocol
91067616 Rev/Ver AK
Page 21 of 64

Technical Success

8. Ability to deploy the stent in satisfactory position (Stent Placement Success).

Satisfactory position is defined as the stent being across the stricture, without visible occluding impaction at the genu of the pancreatic duct and with distal end of the stent visible in the duodenum. Ease of placement will also be assessed.on a 5 point Likert scale.

9. Successful endoscopic stent removal (Endoscopic Stent Removal Success).

Endoscopic stent removal success is defined as ability to remove stent endoscopically (forceps, snare) without serious stent removal-related adverse events. Ease of removal will also be assessed.on a 5 point Likert scale. Use of stent-in-stent removal technique will be considered a removal failure. If stent migration is noted at time of study stent removal, the patient will be excluded from this endpoint's analysis.

Safety and Device Events

10. Device Events, including findings not associated with adverse events, such as but not limited to asymptomatic stent migration.

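### The synopsis and section 4.3 give different exclusion rules for Endoscopic Stent Removal Success, so the denominator of this secondary endpoint is not settled

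*Combined protocol and SAP*

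**What the plan says.** The definition of success is the same in the synopsis and in section 4.3: "Endoscopic stent removal success is defined as ability to remove stent endoscopically (forceps, snare) without serious stent removal-related adverse events". Both also state: "Use of stent-in-stent removal technique will be considered a removal failure". They differ on who is left out.

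- **Synopsis, Secondary Endpoints, item 9:** "For patients who experience complete distal migration of the study stent, this endpoint will not be evaluated".
- **Section 4.3, item 9:** "If stent migration is noted at time of study stent removal, the patient will be excluded from this" analysis.

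Section 8 (Statistical Considerations) restates the primary endpoints but not the secondary ones. Both rules are current text, and nothing ranks one above the other.

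Elsewhere the protocol treats partial migration as a category of its own. For endpoint 4, section 4.3 says: "Stent functionality will be assessed from stent placement until stent removal or observation of complete or partial stent migration".

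**The concern.** After complete distal migration no stent is left in the duct, so there is nothing to score. That is the case the synopsis excludes. A stent that has migrated partially or proximally is still in the patient and has to be retrieved. Section 4.3 drops that patient as well, on the strength of a finding made at the removal procedure itself. If the retrieval then needs a stent-in-stent technique or causes a serious removal-related event, the synopsis rule counts a failure and section 4.3 counts nothing.

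The mismatch also runs the other way. Section 4.3 speaks only of migration noted at the time of removal. Read literally, it does not say what happens to a patient whose complete distal migration was seen at an earlier visit; the synopsis does cover that patient.

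At stake are the reported success rate for removing a temporary stent, the number of patients behind it, and the fact that the denominator could be chosen after the data are seen.

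**Working it through.** The documents give no target, rate or sample size for this endpoint, so there is no stated figure to reproduce. The check compares the two rules case by case and then illustrates the size of the difference.

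**Step 1. The rules side by side**

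| Situation | Synopsis | Section 4.3, read literally |
|---|---|---|
| No migration, stent removed | Counted | Counted |
| Complete distal migration first noted at the removal visit | Not evaluated | Excluded |
| Complete distal migration seen earlier | Not evaluated | Not addressed |
| Partial or proximal migration noted at removal, stent still to be removed | Counted, including failures | Excluded, including failures |

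The rules part company in the last two rows.

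**Step 2. How often migration might arise**

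Section 1.2 reports a 10-patient pilot: "Clinically meaningful complete distal migration (CDM) with symptoms occurred in 25% (3/12) of stent placements with intended stent indwell". It also says that migration without symptoms "occurred in 6 stent placements, not requiring restenting". Together that is (3 + 6)/12 = 75% of placements with intended indwell. Three per-protocol endoscopic removals are reported, which is consistent with the remaining 12 − 9 = 3. The text does not say how many of the 6 were partial, so the rules could differ on anything from 0 to 6 of 12 placements.

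**Step 3. Illustration**

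Inputs:

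- N = 92, the enrolment ceiling (section 4.4).
- Complete distal migration 25%, borrowed from the pilot's symptomatic figure.
- Failure in non-migrated stents 3%, borrowed from the 2/71 removals needing stent-in-stent in the metal-stent literature (section 1.1).
- Other migration noted at removal, m = 5%, 10% or 25%. This is assumed; the documents give no figure for this device.
- Failure in those migrated stents, f = 3%, 10% or 30%. This is also assumed.

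Formulas:

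- Synopsis denominator = 92 × (1 − 0.25) = 69.
- Section 4.3 denominator = 92 × (1 − 0.25 − m).
- Section 4.3 success = 1 − 0.03 = 97.0% in every case.
- Synopsis success = [92(0.75 − m) × 0.97 + 92m × (1 − f)] / 69.

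| m | Section 4.3 denominator | Synopsis success, f = 3% | f = 10% | f = 30% |
|---|---|---|---|---|
| 5% | 64.4 | 97.0% | 96.5% | 95.2% |
| 10% | 59.8 | 97.0% | 96.1% | 93.4% |
| 25% | 46.0 | 97.0% | 94.7% | 88.0% |

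Worked case, m = 25% and f = 30%: (46 × 0.97 + 23 × 0.70)/69 = (44.62 + 16.10)/69 = 88.0%.

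Failures that section 4.3 leaves uncounted = 92 × m × f. This runs from 4.6 × 0.03 = 0.1 patients to 23 × 0.30 = 6.9 patients.

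**Step 4. If migrated stents fail no more often**

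With f = 3% the two rules give the same rate and only precision differs. The standard error is √(0.97 × 0.03/69) = 2.1 percentage points under the synopsis rule, against √(0.97 × 0.03/46) = 2.5 points under section 4.3 at m = 25%.

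**The case against.** The strongest reply is that the discrepancy is one of wording and that no harm has been shown. No section says migrated stents are harder to remove. The pilot had no proximal migrations, and section 1.2 reads symptom-free migration as a sign that the stricture was adequately calibrated. Section 2.1 describes a duodenal flare meant to prevent inward migration. The 5.2% proximal rate quoted in section 1.1 is for pancreatic stents in general. The endpoint has no hypothesis test. Serious events related to removal or migration still count in the primary safety endpoint (section 4.2), and migration itself is recorded under secondary endpoint 10.

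Most of this stands, and it limits the point to what section 4.3 could do. It does not remove the contradiction. It also leaves one outcome uncovered: a stent-in-stent removal without a serious adverse event is a failure of this endpoint but would not reach the primary safety endpoint.

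A reader might infer something stronger: that section 4.3 drops the removals most likely to fail, and that scaling the pilot to 92 patients shows a large bias. If all 6 symptom-free migrations were partial (50% of placements) and removal succeeded in 85% of such stents, the synopsis rule would give (23 × 0.97 + 46 × 0.85)/69 = 89%, against 97% under section 4.3. The documents do not support this. The 85% has no source. Section 1.2 does not call any of the 6 partial, and it times follow-up only from removal or complete distal migration. If all 6 were complete and noted at removal, both rules would leave about 23 of 92 patients and would not differ. The pilot proportions also come from 12 placements in 10 patients, including second stents placed after migration, which section 4.6 does not allow here.

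**Conclusion.** The contradiction is certain: two current passages define different denominators for the same endpoint, and neither overrides the other. Section 4.3 makes a post-treatment finding a reason to exclude patients who can still succeed or fail.

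Whether this biases the result is not established. On the assumptions shown, the overstatement under section 4.3 runs from nil, if migrated stents fail at the same 3%, to 97.0 − 88.0 = 9.0 percentage points, if a quarter of patients have other migration and 30% of those removals fail. The 3% comes from other metal stents and counts only stent-in-stent removals. The 25% comes from a very small pilot. The share and failure rate of partially or proximally migrated stents are assumed.

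This is a point to correct in a descriptive secondary endpoint. It does not touch either primary endpoint or the sample size.

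**What to change.** Use one rule in the synopsis and in section 4.3:

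- Exclude from the removal-success analysis only patients with complete distal migration, where no stent is left to remove, whether this is seen at the removal visit or before it.
- Keep in the denominator every partially or proximally migrated stent that undergoes removal, with the existing success and failure definitions.
- Tabulate removal success, and the number of patients excluded, by migration type.

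The cost is one sentence in section 4.3, a matching clarification in the synopsis and one additional table. No procedure changes. The reported success rate may come out somewhat lower than under section 4.3. The change should be made before the removal data are analysed, so that the choice of denominator cannot follow the results.

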4.4 Study Design

This study is a prospective, single arm, pre-approval study. Treatment of up to 92 patients will take place at up to 15 clinical centers. Patient who meet all eligibility criteria will receive the WallFlex Pancreatic stent for up to 6 months stent indwell and 6 months follow-up after stent removal.

4.5 Stent Removal

Stent removal will be performed using a rat-tooth forceps to grasp the retrieval loop on the end of the stent. The stent is gently pulled back with the scope to remove. Forceps, grasper, snare or stent-in-stent technique may be utilized for removal.

Stent removal will be planned after 6 months of stent indwell. Early stent removal may be prompted by increased pain that the investigator deems not to be adequately managed with medication.

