Use of self-expanding metal stents (SEMS) in benign main PD strictures associated with painful chronic pancreatitis (CP) was first described in the 1990s, culminating in a recommendation¹² that use of uncovered SEMSs in the PD should be avoided and that use of covered SEMSs (CSEMSs) in the PD holds promise in this indication. Compared to resective or bypass surgery, the use of SEMS is less invasive. Compared to MPS, the use of SEMS is anticipated to result in similar long-term stent-free pain relief, however requiring a shorter duration of stent therapy and fewer ERCPs. Literature-based values are summarized below.

August 28, 2017

Boston Scientific
WallFlex Pancreatic Pivotal Protocol
91067616 Rev/Ver AK
Page 15 of 64

Table 1.1-1: Plastic Stent Literature Values

Study	Number of ERCPs	Total PS indwell duration
Eleftheriadis 2005 ²	Median 3 Range 1-18	Median 23 months Range 2-134 months
Vitale 2004 ³	Mean 4.1	Range 3-12 months
Topazian 2005 ⁴	Mean 3.2	Intended 6 months, actual duration not reported
Costamagna 2006 ⁵	Not reported	Mean 7 months Range 5-11 months
Farnbacher 2006 ⁶	Not reported	Mean 10 months±10 months
Ishiara 2006 ⁷	Not reported	Mean 335±31 days
Cahen 2007 ⁸	Median 5 Range 1-11	Mean 27 weeks Range 6-67
Weber 2007 ⁹	Not reported	Mean 5.6 months Range 1-1- months
Seza 2011 ¹⁰	Not reported	Mean 15.2±3.1 months
Gabrielli 2005 ¹¹	Not reported	Not reported

A literature review of 2000-2012 yielded 5 publications with series of 5 or more cases totaling 72 cases¹³⁻¹⁷ pertaining to benign PD stricture resolution after treatment using CSEMS. After stent indwell ranging from 2 to 9 months, CSEMS removal was attempted in 71 patients and was achieved without difficulty in 97% (69/71). In 3% (2/71) CSEMS were embedded and required a stent-in-stent technique for subsequent removal. Overall clinical success after post stent removal follow-up ranging from 4 to 20 months averaged 83% (59/71) (range 40%-100%). The overall reintervention rate was 18% (13/72) (range 8%-45%). There were 22 reported stent-related complications in 72 patients, including immediate post FCSEMS placement pain that may require stent removal in some patients.

Of note are publications by the American Society of Gastroenterological Endoscopy (ASGE) and the European Society of Gastroenterological Endoscopy (ESGE) on endotherapy in patients with painful CP:

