4.1 Primary Effectiveness Endpoint

Pain Reduction

Pain reduction will be assessed at 6 months post-stent removal or 6 months post-observation of complete or partial stent migration compared to pain collected at baseline. Baseline for patients without a plastic pancreatic stent immediately prior to study stent placement will be at the time of enrollment. Baseline for patients with a plastic pancreatic stent immediately prior to study stent placement will be at the time of study stent placement.

Pain will be scored between 0 and 100 as the mean of the VAS Pain Score and Frequency of Pain sectors of the Izbicki pain scale.

Complete pain relief is defined as pain score ≤ 10 , and partial pain relief is defined as pain score > 10 and reduced by at least 50% compared to baseline.

August 28, 2017

Boston Scientific
WallFlex Pancreatic Pivotal Protocol
91067616 Rev/Ver AK
Page 19 of 64

Complete or partial pain relief in the setting of a 50% higher average daily narcotic dose will be considered a primary effectiveness endpoint failure. Average daily narcotic dosage for prior month will be assessed at baseline visit prior to plastic or study stent placement, whichever is implanted first, and at 6 months post-stent removal/observation of complete distal migration.

Patients who experience stent migration in setting of recurring pain (VAS Pain Score of ≥ 20) will be considered as having failed the primary effectiveness endpoint.

Patients who are restented in the setting of recurring pain will be considered as having failed both the primary effectiveness endpoint and the secondary endpoint for stricture resolution and may only be restented with a non-study stent.

Restenting with a new study stent may only occur during the initial stent placement procedure for such situations as stent misplacement, improper stent size choice, or other conditions, as necessary and will not be considered a primary effectiveness endpoint failure or a secondary effectiveness stricture resolution endpoint failure.

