8.1 Endpoints

8.1.1 Primary Endpoint

Primary Effectiveness Endpoint:

Pain Reduction

Pain reduction will be assessed at 6 months post-stent removal or 6 months post-observation of complete or partial stent migration compared to pain collected at baseline. Baseline for patients without a plastic pancreatic stent immediately prior to study stent placement will be at the time of enrollment. Baseline for patients with a plastic pancreatic stent immediately prior to study stent placement will be at the time of study stent placement.

Pain will be scored between 0 and 100 as the mean of the VAS Pain Score and Frequency of Pain sectors of the Izbicki pain scale.

Complete pain relief is defined as pain score ≤ 10 , and partial pain relief is defined as pain score > 10 and reduced by at least 50% compared to baseline.

Complete or partial pain relief in the setting of a 50% higher average daily narcotic dose will be considered a primary effectiveness endpoint failure. Average daily narcotic dosage for prior month will be assessed at baseline visit prior to plastic or study stent placement, whichever is implanted first, and at 6 months post-stent removal/observation of complete distal migration.

Patients who experience stent migration in setting of recurring pain (VAS Pain Score of ≥ 20) will be considered as having failed the primary effectiveness endpoint.

Patients who are restented in the setting of recurring pain will be considered as having failed both the primary effectiveness endpoint and the secondary stricture resolution endpoint and may only be restented with a non-study stent.

Restenting with a new study stent may only occur during the initial stent placement procedure for such situations as stent misplacement, improper stent size choice, or other conditions, as necessary and will not be considered a primary effectiveness endpoint failure or a secondary effectiveness stricture resolution endpoint failure.

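### Early stent removal for increased pain not controlled by medication is not a primary effectiveness failure, although migration or restenting with recurring pain is

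*Combined protocol and SAP*

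**What the plan says.** Section 4.5 sets the intended indwell: "Stent removal will be planned after 6 months of stent indwell". It then allows an exception: "Early stent removal may be prompted by increased pain that the investigator deems not to be adequately managed with medication". It does not say what caused the pain, and it gives no consequence for the primary endpoint.

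Section 4.1 sets the time point: "Pain reduction will be assessed at 6 months post-stent removal or 6 months post-observation of complete or partial stent migration". The clock starts at removal or migration whenever that happens, and no minimum indwell is required. Section 8.1.1 repeats this. Success is a pain score of 10 or less (complete relief), or partial relief, where "partial pain relief is defined as pain score > 10 and reduced by at least 50% compared to baseline".

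Three rules in the synopsis, 4.1 and 8.1.1 turn a good pain score into a failure:

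- Narcotics: "Complete or partial pain relief in the setting of a 50% higher average daily narcotic dose will be considered a primary effectiveness endpoint failure".
- Migration: "Patients who experience stent migration in setting of recurring pain", with a VAS score of 20 or more, are failures.
- Restenting in the setting of recurring pain is a failure.

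Removal for uncontrolled pain is not on the list. Section 4.2 deals with pain that leads to removal on the safety side only: stent-expansion pain is exempt from the related-SAE endpoint under three conditions, one of which is that it did not lead to removal.

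Section 1.1 shows that removal for pain is foreseeable. Among reported complications of covered metal stents it lists "immediate post FCSEMS placement pain that may require stent removal in some patients", without a rate. Section 1.2 reports no removal for intolerable pain after placement in the 10-patient pilot.

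**The concern.** The plan already treats some ways of losing or replacing the stent with pain as failure in themselves. A patient whose stent migrates with recurring pain fails even if pain-free 6 months later. A patient whose stent the investigator takes out because pain could not be controlled is judged on the later score alone. Both stents were lost with pain, but the scoring differs.

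After an early removal, later relief may come from other treatment or from the course of the disease. Apart from the narcotic rule and restenting for recurring pain, no rule separates that relief from an effect of the study stent. The trial has one arm and a fixed performance goal of 53%, so there is no control group in which the same credit would arise. Any such patient adds directly to the observed success rate.

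**Working it through.** **1. The plan's own figure.** Inputs from 8.1.2 and the synopsis: null rate 53%, assumed rate 75%, exact test, one-sided alpha 0.025, power 80%, stated N=43. The rule is to reject when the number of successes X reaches r, the smallest count with P(X ≥ r | N, 0.53) ≤ 0.025.

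- N=43: r=30, alpha 0.019, power P(X ≥ 30 | 43, 0.75) = 0.834.
- N=42: r=30, power 0.766.

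The stated 43 is reproduced. The sample size is not in question.

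**2. The planned number.** Section 8.1.2 aims for 64 patients who meet the pain levels at study stent placement. At N=64, r=43, alpha is 0.015 and power is 0.940.

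**3. How one patient is scored.** Each patient below has a pain score at least halved 6 months later and no 50% higher narcotic dose.

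| Event during indwell | Score under 8.1.1 |
|---|---|
| Migration with recurring pain, VAS of 20 or more | Failure |
| Restented for recurring pain | Failure |
| Removed early for uncontrolled pain, not restented for recurring pain | Success |

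**4. Effect on the chance of meeting the goal.** Let e be the share of all analysed patients who are removed early for uncontrolled pain and later scored as successes. The documents do not give e, so the values are assumptions. Suppose the true success rate is 53% when these patients count as failures. Current scoring then has a success probability of 0.53 + e, and the chance of meeting the goal at N=64 is P(X ≥ 43 | 64, 0.53 + e).

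| e | Rate under current scoring | Chance of meeting the goal |
|---|---|---|
| 0% | 53% | 0.015 |
| 1% | 54% | 0.022 |
| 3% | 56% | 0.045 |
| 8% | 61% | 0.188 |

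Of 64 patients, 3% is about 2 (0.03 × 64 = 1.9) and 8% is about 5 (0.08 × 64 = 5.1).

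**5. Cost of the stricter scoring.** If current scoring gives 75% and share e moves to failure, power at N=64 is P(X ≥ 43 | 64, 0.75 − e): 0.940 at 0%, 0.841 at 3% and 0.546 at 8%.

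**6. How many patients would change a result.** At the assumed 75%, 48 of 64 succeed. Moving 5 leaves 43, which still meets the goal; moving 6 leaves 42, which does not. At N=43, 32 succeed; moving 2 leaves 30, which meets it, and moving 3 leaves 29, which does not.

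**7. What is known about e.** The pilot saw 0 of 10 removals for intolerable pain. The exact two-sided 95% upper limit is 1 − 0.025^(1/10) = 0.31. That bounds removals, not removals later scored as successes, and it is too wide to support any particular value.

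**The case against.** The strongest case is that the present scoring is a deliberate and defensible choice. Section 4.4 describes an indwell of up to 6 months, so a short indwell is not in itself a failure, and section 1.2 reads symptom-free migration as a possible sign of adequate calibration. Scoring observed pain in everyone, whatever the indwell, is a legitimate treatment-policy approach. Pain from stent expansion is a tolerability matter, and section 4.2 brings it into the safety endpoint when it leads to removal. The existing rules also narrow the case: section 4.6 calls for restenting when clinical status has not improved and the stricture persists on imaging, and restenting for recurring pain is a failure. Stent functionality, a secondary endpoint, would be expected to show the event.

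Much of this stands as a limit on the point. It does not remove it. The safety endpoint counts the event only if it is a related SAE, and only toward the safety rate. The secondary endpoints carry no stated hypothesis test. The treatment-policy argument would apply equally to migration with pain, where the plan has chosen failure.

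Other objections concern the remedy. Failing every such removal would include a patient whose stent came out in month 5 and who is pain-free 6 months later. It would also tie a discretionary decision to endpoint failure. And the documents do not show how the ten studies behind the 53% goal scored early removal. These are reasons to report both scorings.

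A reader might infer that stents which caused intolerable pain are being scored as successes. Section 4.5 does not support that: it speaks of increased pain without giving a cause, and disease pain would qualify too. Nor is every early removal scored a success, since relief is still required and the narcotic and restenting rules still apply.

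**Conclusion.** The gap is in the text: three overrides are listed, and early removal for uncontrolled pain is not among them. The scoring is inconsistent with the migration and restenting rules, and its direction is upward.

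Its size is unknown and may be near zero. The probabilities rest on two assumptions: the share e, and the view that these removals are failures. A reader might infer that the planned test exceeds its stated error rate. It does not: under the protocol's own definition of success the exact test at N=64 has a level of 0.015. Even when such removals are regarded as failures, a 1% share leaves the chance at 0.022, still below 0.025; at 3% it is 0.045.

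The point is worth settling before the data are seen, because the change is small and a later choice would be open to dispute.

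**What to change.** In the synopsis, 4.1 and 8.1.1, add a rule beside those for migration and restenting: a patient whose study stent is removed before the Month 6 removal window because of increased pain not adequately managed with medication is a primary effectiveness failure. Record the reason for each removal on the case report form. Report the primary result both ways, with these patients as failures and on their observed 6-month pain score.

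The change takes one sentence in three places, one data field and one extra analysis. The downside is a somewhat lower observed success rate and lower power if such removals occur: at N=64, from 0.94 to 0.84 for a 3% share, with a larger loss if the share is larger. The change concerns endpoint scoring only; the clinical rule for when to remove a stent stays as it is.
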